Any SAEs experienced after the 30 day period after the last study visit should only be reported to Novartis Safety if the investigator suspects a causal relationship to study treatment, unless otherwise specified by local law/regulations.

Treatment-emergent elevations in AST or ALT ($>3x$ ULN) in combination with total bilirubin $>2x$ ULN or jaundice in the absence of cholestasis (defined as ALP <2 ULN) or other causes of hyperbilirubinemia can be an indicator of severe drug induced liver injury (Hy's Law). For this reason, a potential Hy's Law case requires expedited reporting, and will be handled as a serious unexpected adverse event (assessing it as medically significant in the absence of any other seriousness criteria). It must be reported as an SAE to the sponsor promptly (i.e., even before all other possible causes of liver injury have been excluded). Reporting should include all available information, especially that needed for evaluating the diagnosis, severity and likelihood that the study treatment caused the reaction. For patient monitoring and to better understand potential etiologies, the investigator must initiate a close follow-up until complete resolution of the problem and completion of all attempts to obtain supplementary data.

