16.2 Appendix 2: Liver laboratory triggers & follow-up monitoring requirements

16.2.1 Liver laboratory triggers

Liver laboratory triggers which require follow-up monitoring include:

- ALT > 3 × ULN
- TBL > 1.5 × ULN (in the absence of known Gilbert's syndrome)
- Potential Hy's Law cases (defined as ALT or AST > 3 × ULN and TBL > 2 × ULN [mainly conjugated (direct) fraction] without notable increase in ALP to > 2 × ULN)

16.2.2 Follow up requirements for liver laboratory triggers – ALT and AST, with and without TBL

Table 16-1 Follow-up requirements for liver laboratory triggers – ALT and AST, with and without TBL

ALT	TBL	Liver Symptoms	Actions/Follow-up Monitoring
ALT > 3 x ULN	
 • Normal • For participants with Gilbert's syndrome: No change in baseline TBL 	None	
 • Review compliance with immunomodulatory therapy (Section 6.2) • Measure ALT, AST, TBL, fractionated bilirubin (direct and indirect), INR, and GLDH within 48-72 hours • Follow-up for symptoms
ALT > 5 x ULN	
 • Normal • For participants with Gilbert's syndrome: No change in baseline TBL 	With or without symptoms	
 • Review compliance with immunomodulatory therapy (Section 6.2) • Measure ALT, AST, TBL, fractionated bilirubin (direct and indirect), INR, albumin, CK, and GLDH within 48 - 72 hours • Follow-up for symptoms • Initiate close monitoring (hospitalization when appropriate) and workup for competing etiologies^a • Exclude underlying liver disease • Obtain detailed history of concomitant medications (e.g. acetaminophen) • Consult pediatric gastroenterologist^b
ALT or AST > 3 x ULN	
 • TBL > 2 x ULN (or INR > 1.5) • For participants with Gilbert's syndrome: Doubling of direct bilirubin 	With or without symptoms	
ALT > 3 x ULN	Normal or elevated	Severe fatigue, nausea, vomiting, and/or right upper quadrant pain	

^a Work-up for competing etiologies may include (but not limited to) viral hepatitis panel (IgM anti-HAV; HBsAg, IgM anti-HBc, hepatitis B virus (HBV) DNA, hepatitis C virus (HCV) ribonucleic acid (RNA), anti-HCV, IgM & IgG, hepatitis E virus (HEV) RNA, anti-HEV, viral panel (CMV, EBV, HSV), autoimmune hepatitis (ANA, anti-smooth muscle antibody (ASMA) titers)

^b Consider appropriate imaging and liver biopsy in consultation with a pediatric gastroenterologist

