Week 52 + Day 1	Day 1	Day 1	Day 1	Day 1
Week 52 + Day 2	Day 2	Day 2	Day 2	Day 2
Week 53	Week 1	Day 8	Day 3	Day 18
Week 56	Week 4	Day 29	Day 19	Day 43
Week 60	Week 8	Day 57	Day 44	Day 71
Week 64	Week 12	Day 85	Day 72	Last participation day

Body Height (Segmental by Tibial Length) and BMI:

Period 1 windows:

Visit	Nominal day	Start day	End day
Week 4	Day 29	Day 1	Day 43
Week 8	Day 57	Day 44	Day 71
Week 12	Day 85	Day 72	Day 127
Week 24	Day 169	Day 128	Day 211
Week 36	Day 253	Day 212	Day 295
Week 48	Day 337	Day 296	Day 351
Week 52	Day 365	Day 352	Week 52 + Day 1 – 1

Period 2 windows:

Visit (OAV-SHAM)	Visit (SHAM-OAV)	Nominal day	Start day	End day
Week 56	Week 4	Day 29	Day 1	Day 43
Week 60	Week 8	Day 57	Day 44	Day 71
Week 64	Week 12	Day 85	Day 72	Last participation day

Hematology and Clinical Chemistry:

Period 1 windows:

Visit	Nominal day	Start day	End day
Week 1	Day 8	Day 1	Day 11
Week 2	Day 15	Day 12	Day 18
Week 3	Day 22	Day 19	Day 25
Week 4	Day 29	Day 26	Day 36
Week 6	Day 43	Day 37	Day 50
Week 8	Day 57	Day 51	Day 64
Week 10	Day 71	Day 65	Day 78
Week 12	Day 85	Day 79	Day 99
Week 16	Day 113	Day 100	Day 127
Week 20	Day 141	Day 128	Day 155
Week 24	Day 169	Day 156	Day 183
Week 28	Day 197	Day 184	Day 211
Week 32	Day 225	Day 212	Day 239
Week 36	Day 253	Day 240	Day 267
Week 40	Day 281	Day 268	Day 295
Week 44	Day 309	Day 296	Day 323
Week 48	Day 337	Day 324	Day 351
Week 52	Day 365	Day 352	Week 52 + Day 1 – 1

Period 2 windows:

Visit (OAV-SHAM)	Visit (SHAM-OAV)	Nominal day	Start day	End day
Week 53	Week 1	Day 8	Day 1	Day 11
Week 54	Week 2	Day 15	Day 12	Day 18
Week 55	Week 3	Day 22	Day 19	Day 25
Week 56	Week 4	Day 29	Day 26	Day 36

Visit (OAV-SHAM)	Visit (SHAM-OAV)	Nominal day	Start day	End day
Week 58	Week 6	Day 43	Day 37	Day 50
Week 60	Week 8	Day 57	Day 51	Day 64
Week 62	Week 10	Day 71	Day 65	Day 78
Week 64	Week 12	Day 85	Day 79	Last participation day

HFMSE, RULM CCI : [REDACTED]

Period 1 windows:

Visit	Nominal day	Start day	End day
Week 4	Day 29	Day 1	Day 43
Week 8	Day 57	Day 44	Day 71
Week 12	Day 85	Day 72	Day 99
Week 16	Day 113	Day 100	Day 127
Week 20	Day 141	Day 128	Day 155
Week 24	Day 169	Day 156	Day 183
Week 28	Day 197	Day 184	Day 211
Week 32	Day 225	Day 212	Day 239
Week 36	Day 253	Day 240	Day 267
Week 40	Day 281	Day 268	Day 295
Week 44	Day 309	Day 296	Day 323
Week 48	Day 337	Day 324	Day 351
Week 52	Day 365	Day 352	Week 52 + Day 1 – 1

[figure not shown]
Period 2 windows:

Visit (OAV-SHAM)	Visit (SHAM-OAV)	Nominal day	Start day	End day

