The shift tables will cross tabulate the frequency (number and percentage) of participants with baseline versus post-baseline level. These summaries will be presented by laboratory test and treatment group for overall. The shift tables will present shifts from baseline to each visit and to final value. Moreover, for laboratory parameters based on CTC grade, shift tables from baseline to the worst CTC grade level at any time post-baseline will be generated. Participants with specific laboratory abnormalities (defined by CTC grade 3 and 4) will be listed. For laboratory parameters based on Low/Normal/High range, shift tables from baseline to the maximum at any time post-baseline will be generated.

A second set of shift tables will be produced to summarize the shifts from baseline to the maximum value, and final values as well as shift tables based on CTCAE grades from baseline to worst post-baseline values reported after treatment with OAV101. In this second set of outputs, only laboratory values reported on/after OAV101 dosing (during Treatment Period 1 and through the end of study for participants originally randomized to OAV101, during Treatment Period 2 and through the end of study for participants originally randomized to sham administration) will be considered.

The number and percentage of participants meeting each of the following criteria through the end of Follow-up Period 1 will be summarized:

- Alanine aminotransferase (ALT) >2x upper limit of normal (ULN), ALT >3x ULN, ALT >5x ULN, ALT >8x ULN, ALT >10x ULN, ALT >20x ULN
- Aspartate aminotransferase (AST) >2x ULN, AST >3x ULN, AST >5x ULN, AST >8x ULN, AST >10x ULN, AST >20x ULN
- ALT or AST >2x ULN, ALT or AST >3x ULN, ALT or AST >5x ULN, ALT or AST >8x ULN, ALT or AST >10x ULN, ALT or AST >20x ULN

- Total bilirubin $>1.5 \times$ ULN, $>2 \times$ ULN, Total bilirubin $>3 \times$ ULN
- ALT or AST $>3 \times$ ULN and Total bilirubin $>2 \times$ ULN
- ALT or AST $>3 \times$ ULN and Total bilirubin $>2 \times$ ULN and Alkaline phosphatase (ALP) $\geq 2 \times$ ULN
- ALT or AST $>3 \times$ ULN and Total bilirubin $>2 \times$ ULN and ALP $<2 \times$ ULN

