A participant or event will be counted if the post-baseline laboratory values meet the above criteria regardless of the baseline laboratory value (i.e., the post-baseline laboratory value does not need to be worse than the baseline laboratory value). For the last three combination categories, the values do not need to have been collected at the same assessment. For participants meeting any elevation criterion, a corresponding listing of all ALT, AST, ALP, INR, GLDH and total, direct, and indirect bilirubin values will be provided.

Additionally, a summary will be produced to detail the number and percentage of participants with post-baseline, post-OAV101 treatment values meeting the specified criteria outlined above. In this second summary, only laboratory values reported on/after OAV101 dosing (during Treatment Period 1 and through the end of study for participants originally randomized to OAV101, during Treatment Period 2 and through the end of study for participants originally randomized to sham administration) will be considered.

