2.7.4 Other safety data

2.7.4.1 ECG and cardiac imaging data

A 12-lead ECG and standard transthoracic ECHO will be conducted at the scheduled visits in accordance with the Schedule of Study Assessments. ECGs and ECHOs will be interpreted locally by a cardiologist for immediate safety evaluation. The ECG tracings or ECG machine data and ECHOs will also be collected for centralized review and interpretation by a cardiologist. For continuous ECG parameters, the mean value for each visit will be calculated from the triplicate ECGs for each participant. For categorical ECG parameters, the worst value from the triplicate ECGs for each visit will be used for each participant. The SAF will be used for all summaries of data.

For 12-lead ECG, observed values as well as change from baseline values will be summarized at each scheduled visit through the end of Follow-up Period 1 using descriptive statistics for the following parameters as measured by the central reviewer: RR, PR, QRS, QT, and QT interval corrected by Fridericia's formula (QTcF). Additionally, a summary of ECG interpretation (normal, abnormal) at each scheduled visit through the end of Follow-up Period 1 will be provided and a summary (number and percentage of participants) of participants meeting the following criteria at anytime post baseline will be provided.

- New maximum QTcF value: > 450 msec to ≤ 480 msec, > 480 msec to ≤ 500 msec and > 500 msec. For criteria based on only absolute values, patients must have post baseline value for that parameter and missing baseline or baseline value not meeting the criteria as below.
 - New > 450 to ≤ 480 msec means baseline ≤ 450 .
 - New > 480 to ≤ 500 msec means baseline ≤ 480 .

- New > 500 msec means baseline ≤ 500 .
- Maximum increase from baseline in QTcF: > 30 msec to ≤ 60 msec, > 60 msec.

A similar, second set of outputs will be produced, considering just the post-baseline, post-OAV101 treatment values. In these second summaries, only ECG values reported on/after OAV101 dosing (during Treatment Period 1 and through the end of study for participants originally randomized to OAV101, during Treatment Period 2 and through the end of study for participants originally randomized to sham administration) will be considered.

For ECHO, the following data will be summarized by treatment, considering post-baseline data through the end of Follow-up Period 1:

- Number and percentage of participants with intracardiac thrombi

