5.3 Laboratory parameters derivations

Hy's law criteria apply (see [Section 2.7.3](#)).

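### As written, any single ALP value below 2× ULN satisfies the SAP's Hy's law row, so that row nearly repeats the row without ALP and counts cholestatic episodes

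*SAP*

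**What the plan says.** SAP 2.7.3 (Laboratory data) introduces a list of liver criteria with: "The number and percentage of participants meeting each of the following criteria through the end of Follow-up Period 1 will be summarized". The last three are combinations:

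- **Base row:** ALT or AST >3× ULN and TBL >2× ULN.
- **ALP-high row:** the base row plus ALP ≥2× ULN.
- **ALP-low row:** the base row plus ALP <2× ULN.

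A participant counts when post-baseline values meet the criteria, whatever the baseline value. The timing rule is: "For the last three combination categories, the values do not need to have been collected at the same assessment". No sentence links ALP to the ALT/AST or TBL rise. A second summary applies the same criteria to values on or after OAV101 dosing.

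SAP 5.3 says only "Hy's law criteria apply" and refers back to 2.7.3, where the ALP-low row is the only one that requires ALP below 2× ULN.

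The protocol describes the pattern twice. Section 10.2.2 has the elevations occurring "in the absence of cholestasis (defined as ALP <2 ULN". Section 16.2.1 has them "without notable increase in ALP to > 2 × ULN".

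**The concern.** ALT/AST >3× and TBL >2× are upper thresholds. Letting them be met at different times makes the screen sensitive, at the price of some false positives. ALP <2× is a criterion of absence, and almost anyone meets it at some visit. Applying the same any-assessment rule to it removes its power to exclude.

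The ALP-low row then no longer separates a hepatocellular pattern from a cholestatic one, which is its only purpose beside the base row. Hepatotoxicity is the first AESI listed in both documents, and this row gives the by-arm count a reader would take as the number of Hy's law patterns.

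**Working it through.** The documents state no figure to reproduce. The check is what the written rule does.

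**1. Who is kept out of the ALP-low row?**
- The chemistry windows in SAP 2.1.2 ("Hematology and Clinical Chemistry") are Weeks 1, 2, 3, 4, 6, 8, 10 and 12 (8 windows), then every four weeks from Week 16 to Week 52 (10 windows). That is 8 + 10 = 18 in Period 1. Period 2 has 8.
- Protocol 8.4.1.4 includes ALP in the chemistry panel with ALT, AST and total bilirubin.
- A base-row participant with usable ALP is outside the ALP-low row only if ALP is ≥2× on every post-baseline draw. With a complete schedule that is 18 of 18 in Period 1.
- In the post-OAV101 summary it is 18 + 8 = 26 of 26 for a participant given OAV101 first and followed through Period 2, and 8 of 8 for one given sham first.
- Any unscheduled repeat adds a further chance of a low ALP.

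**2. Constructed participants.** These are illustrative, not trial data. Each draw is ALT / TBL / ALP in multiples of ULN.

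| Participant | Draws in order | ALP rows as written | ALP rows under the fix below |
|---|---|---|---|
| A: cholestatic episode | 1/0.5/0.8; 5/2.5/3.0; 2/1.2/1.6; 0.8/0.6/0.9 | high and low | high only |
| B: Hy's law pattern, later separate ALP rise | 1/0.5/0.8; 6/2.6/1.2; 2/1.0/1.3; 0.9/0.6/2.3 | high and low | low only |
| C: Hy's law pattern, ALP always low | 1/0.5/0.8; 6/2.6/1.2; 2/1.0/1.1; 0.9/0.6/0.9 | low only | low only |
| D: ALT and TBL peaks apart, ALP always low | 5/0.6/1.0; 1/0.5/0.9; 1/0.5/0.9; 0.9/2.4/1.1 | low only | low only, footnoted as never concurrent |

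As written, A and B each add 1 to the base, ALP-high and ALP-low rows. The table cannot tell a cholestatic episode from a Hy's law pattern followed by an unrelated ALP rise. Under the fix, A contributes (1, 1, 0) and B contributes (1, 0, 1).

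**3. Two harder patterns.**
- **E:** a cholestatic episode at Week 4 (ALT 4×, TBL 2.5×, ALP 3×), then ALT and TBL above their thresholds with normal ALP at Week 40. As written: both rows. Under the fix: both rows, footnoted. A rule using only the first qualifying draw would give the high row alone and drop the second event.
- **F:** resolving cholestasis, ALP 3× at the episode, then a repeat three days later with ALT 3.5×, TBL 2.2× and ALP 1.9×. Both rows as written and under the fix.

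**4. Size of one reclassification** at the planned arm sizes: 1/75 = 1.33% (OAV101) and 1/50 = 2.00% (sham).

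**The case against.** The strongest reply has three parts.

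- **The overlap may be intended.** The SAP never says the two ALP rows are mutually exclusive, and other rows in the list overlap by design (ALT >2×, >3×, >5×). Because the three rows appear together, the two ALP rows summing to more than the base row would reveal double membership. This stands, and the point does not depend on exclusivity. But the overlap cannot show whether ALP was raised during the episode, as A and B demonstrate.
- **The protocol sets no draw or time window for ALP.** This also stands. That ALP should be judged at the liver event is an inference. It is a strong one, because both protocol passages describe ALP as a feature of the ALT/AST and TBL elevation.
- **The consequence is small.** This stands too. SAP 2.7.3 plans a listing of all liver values for anyone meeting an elevation criterion, and Protocol 10.2.2 requires potential Hy's law cases to be reported as SAEs.

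A reader might go further and infer that ALP could be taken at its peak, so that a later unrelated ALP rise would remove a true Hy's law pattern and make the count too low. The text does not support that. Where the SAP means an extreme it says so, as in "shift tables from baseline to the maximum at any time post-baseline will be generated" and "New maximum QTcF value", and it does not say so here. Under the rule as written, a low ALP at the episode itself qualifies, so no such pattern is lost. The error runs one way: the row counts too many.

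**Conclusion.** The point holds as a minor one. The ALP <2× ULN row is over-inclusive: it nearly equals the row without ALP and counts participants whose only ALT and TBL episode was cholestatic, contrary to the protocol's description of Hy's law.

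Only descriptive counts by arm are affected, in the Period 1 summary and the post-OAV101 summary. The documents give no event rates, so the number miscounted cannot be stated. If no base-row participant ever has ALP ≥2×, the table is the same either way. It would be wrong to infer that cases could go undetected, since the listing and SAE reporting do not depend on this row.

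The conclusion rests on reading SAP 2.7.3 as written. The table shells are not among the documents and might contain a further rule.

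**What to change.** Amend SAP 2.7.3 as follows.

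1. Keep the any-assessment rule for the base row.
2. For the two ALP rows, use ALP only from qualifying draws: every draw with ALT or AST >3× and TBL >2× ULN together or, if there is none, the draw at which the second criterion is first met.
3. If that draw has no ALP, take the nearest post-baseline ALP and footnote the gap in days. This step is needed because the 48–72 hour test lists in Protocol Table 16-1 do not name ALP (the repeat panel in Protocol 10.3.1 does), and SAP 5.1 expects some local results to lack units or normal ranges.
4. Count a participant in the ALP <2× row if ALP is <2× at any qualifying draw, and in the ALP ≥2× row if it is ≥2× at any qualifying draw.
5. Footnote participants in both rows, and those whose ALT/AST and TBL rises were never concurrent.
6. Apply the same rule to the post-OAV101 summary, using only values on or after OAV101 dosing, and keep the full liver listing.

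Using every qualifying draw keeps a later Hy's law pattern (E) that a single index draw would drop.

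The cost is SAP wording and one extra derivation on data already collected. The remaining weakness is that a participant whose ALP falls through 2× ULN within one episode (F) can still appear in both rows, although the footnote will show it.

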2.7.4 Other safety data

2.7.4.1 ECG and cardiac imaging data

A 12-lead ECG and standard transthoracic ECHO will be conducted at the scheduled visits in accordance with the Schedule of Study Assessments. ECGs and ECHOs will be interpreted locally by a cardiologist for immediate safety evaluation. The ECG tracings or ECG machine data and ECHOs will also be collected for centralized review and interpretation by a cardiologist. For continuous ECG parameters, the mean value for each visit will be calculated from the triplicate ECGs for each participant. For categorical ECG parameters, the worst value from the triplicate ECGs for each visit will be used for each participant. The SAF will be used for all summaries of data.

For 12-lead ECG, observed values as well as change from baseline values will be summarized at each scheduled visit through the end of Follow-up Period 1 using descriptive statistics for the following parameters as measured by the central reviewer: RR, PR, QRS, QT, and QT interval corrected by Fridericia's formula (QTcF). Additionally, a summary of ECG interpretation (normal, abnormal) at each scheduled visit through the end of Follow-up Period 1 will be provided and a summary (number and percentage of participants) of participants meeting the following criteria at anytime post baseline will be provided.

- New maximum QTcF value: > 450 msec to ≤ 480 msec, > 480 msec to ≤ 500 msec and > 500 msec. For criteria based on only absolute values, patients must have post baseline value for that parameter and missing baseline or baseline value not meeting the criteria as below.
 - New > 450 to ≤ 480 msec means baseline ≤ 450 .
 - New > 480 to ≤ 500 msec means baseline ≤ 480 .

- New > 500 msec means baseline ≤ 500 .
- Maximum increase from baseline in QTcF: > 30 msec to ≤ 60 msec, > 60 msec.

A similar, second set of outputs will be produced, considering just the post-baseline, post-OAV101 treatment values. In these second summaries, only ECG values reported on/after OAV101 dosing (during Treatment Period 1 and through the end of study for participants originally randomized to OAV101, during Treatment Period 2 and through the end of study for participants originally randomized to sham administration) will be considered.

For ECHO, the following data will be summarized by treatment, considering post-baseline data through the end of Follow-up Period 1:

- Number and percentage of participants with intracardiac thrombi
- Number and percentage of participants with low cardiac function

These parameters are defined as follows:

Intercardiac thrombi: Post-baseline ECHO result of Thrombus present (response of Yes)

Low cardiac function: Post-baseline ECHO results of Left Ventricular Ejection Fraction (LVEF) $< 56\%$ or Left Ventricular Fractional Shortening (LVFS) $< 28\%$

A second output will be produced to detail the number and percentage of participants with intracardiac thrombi and low cardiac function, considering just the post-baseline, post-OAV101 treatment values. In this second summary, only ECHO values reported on/after OAV101 dosing (during Treatment Period 1 and through the end of study for participants originally randomized to OAV101, during Treatment Period 2 and through the end of study for participants originally randomized to sham administration) will be considered.

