1.2 Purpose

The purpose of this phase III multi-center, single dose (1.2×10^{14} vector genomes), randomized, sham-controlled, double-blind trial is to investigate the safety, tolerability, and efficacy of intrathecal (IT) OAV101 in treatment naive, sitting and never ambulatory Type 2 SMA patients ≥ 2 years to < 18 years (Screening Visit 1 must occur before the patient's 18th birthday).

2 Objectives, endpoints and estimands

Objectives and related endpoints are described in [Table 2-1](#).

Table 2-1 Objectives and related endpoints

Objective(s)	Endpoint(s)
Primary objective(s)	Endpoint(s) for primary objective(s)

EFFICACY: To compare the efficacy of OAV101 IT vs. sham control as measured by the change from baseline in HFMSE total score	
Change from baseline in HFMSE total score at the end of Follow-up Period 1 (defined in Section 12.4.1) in the overall study population (≥ 2 to < 18 years age group)
Secondary objective(s)	Endpoint(s) for secondary objective(s)

To compare the efficacy of OAV101 IT vs. sham control in two patient age groups: ≥ 2 to < 5 years (HFMSE, RULM); ≥ 2 to < 18 years (RULM)SAFETY: To evaluate the safety and tolerability of OAV101 IT vs. sham control in patients ≥ 2 to < 18 years	
Change from baseline in HFMSE total score at the end of Follow-up Period 1 in the ≥ 2 to < 5 years age groupAchievement of at least a 3-point improvement from baseline in HFMSE total score at the end of Follow-up Period 1 in the overall study populationAchievement of at least a 3-point improvement from baseline in HFMSE total score at the end of Follow-up Period 1 in the ≥ 2 to < 5 years age groupChange from baseline in RULM at the end of Follow-up Period 1 in the ≥ 2 to < 18 years age groupChange from baseline in the RULM at the end of Follow-up Period 1 in the ≥ 2 to < 5 years age groupIncidence of treatment emergent adverse events (TEAEs) and serious (SAEs)Number of participants with adverse events of special interest (AESIs)Evaluation of changes from baseline in vital signs, physical/neurological examinations, laboratories (chemistry, hematology, liver functions tests), echocardiogram, ECG, anthropometry, and CCINumber (and percentage) of patients with intracardiac thrombiNumber (and percentage) of patients with low cardiac function

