All echocardiogram data will be summarized by treatment and visit/time. Additionally, the following will be summarized:

- Number and percentage of participants with intracardiac thrombi
- Number and percentage of participants with low cardiac function

These parameters are defined as follows:

Intracardiac thrombi: Post-baseline ECHO result of thrombus present (response of Yes)

Low cardiac function: Post-baseline ECHO results of LVEF < 56% or LVFS < 28%

Clinical laboratory evaluations

All laboratory data will be summarized by treatment and visit/time. Shift tables using the low/normal/high classification as well as CTCAE grades will be used to compare baseline to the worst on-treatment value.

CCI

CCI

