1.2 Study Objectives, Endpoints and Estimands

Objective(s)	Endpoint(s)
Primary objective(s)	Endpoint(s) for primary objective(s)

The primary objective of this study is to compare the efficacy of OAV101 IT vs. sham control as measured by the change from baseline in HFMSE total score	
Change from baseline in HFMSE total score at the end of Follow-up Period 1 (defined in Section 2.1.1) in the overall study population (≥ 2 to < 18 years age group)
Secondary objective(s)	Endpoint(s) for secondary objective(s)

To compare the efficacy of OAV101 IT vs. sham control in two patient age groups: ≥ 2 to < 5 years (HFMSE, Revised Upper Limb Module [RULM]); ≥ 2 to < 18 years (RULM)To evaluate the safety and tolerability of OAV101 IT vs. sham control in patients ≥ 2 to < 18 years	
Change from baseline in HFMSE total score at the end of Follow-up Period 1 in the ≥ 2 to < 5 years age groupAchievement of at least a 3-point improvement from baseline in HFMSE total score at the end of Follow-up Period 1 in the overall study populationAchievement of at least a 3-point improvement from baseline in HFMSE total score at the end of Follow-up Period 1 in the ≥ 2 to < 5 years age groupChange from baseline in RULM at the end of Follow-up Period 1 in the ≥ 2 to < 18 years age groupChange from baseline in RULM at the end of Follow-up Period 1 in the ≥ 2 to < 5 years age groupIncidence of treatment-emergent adverse events (TEAEs) and serious adverse events (SAEs)Number of participants with adverse events of special interest (AESIs)Evaluation of changes from baseline in vital signs, physical/neurological examinations, laboratories, (chemistry, hematology, liver function tests), echocardiogram, ECG, anthropometry, and CCI

Objective(s)	Endpoint(s)

• To assess for CCI [REDACTED] in treated patients compared to sham controls in each of three age groups: ≥ 2 to < 18 years, ≥ 2 to < 5 years, and ≥ 5 to < 18 years• To assess for changes CCI [REDACTED] in treated patients compared to sham controls• To assess CCI [REDACTED] post OAV101	
• To assess CCI [REDACTED]• Change from baseline over 52 weeks for CCI [REDACTED]• Evaluation of CCI [REDACTED] in treated patients

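### The low cardiac function count ignores the baseline value, and SAP 2.7.4.1 specifies no LVEF or LVFS change, by-visit or shift output, so pre-existing and new low function cannot be told apart

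*SAP*

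**What the plan says.** Protocol Table 2-1 and SAP 1.2 both list this secondary safety endpoint (quoted from the protocol): "Evaluation of changes from baseline in vital signs, physical/neurological examinations, laboratories (chemistry, hematology, liver functions tests), echocardiogram, ECG, anthropometry". Table 2-1 also has a separate bullet for the number and percentage of patients with low cardiac function.

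Protocol 12.5.2 promises a summary of all echocardiogram data by treatment and visit, and adds two counts: intracardiac thrombi and low cardiac function. The second is defined as "Low cardiac function: Post-baseline ECHO results of LVEF < 56% or LVFS < 28" percent. SAP 2.7.4.1 repeats the rule: "Post-baseline ECHO results of Left Ventricular Ejection Fraction (LVEF) $< 56" percent, or LVFS below 28 percent. Neither text mentions the baseline value.

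For QTcF categories based on absolute values, the same SAP section says that "patients must have post baseline value for that parameter and missing baseline or baseline value not meeting the criteria".

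For echocardiography, SAP 2.7.4.1 specifies the two counts through the end of Follow-up Period 1, and the same two counts again in a second output limited to values after OAV101 dosing. It specifies nothing else.

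**The concern.** A child below a limit before dosing, and below it again afterwards, enters the count exactly as a child whose function fell on study does. The entry criteria do not rule this out. Exclusions 1 and 3 in Protocol 5.2 cover cardiomyopathy and clinically significant test abnormalities by investigator judgement, with no numeric LVEF or LVFS limit.

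A count of this kind is readable if another table shows where children started. Here no specified echocardiogram table does. The converse gap is that a fall in LVEF from 70% to 57% crosses no limit and appears in no echocardiogram output that SAP 2.7.4.1 specifies.

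This bears on a safety question the protocol takes seriously: Section 4.5.3 names cardiac toxicity as an important potential risk. The post-OAV101 output is the most exposed. It pools children dosed in either period and has no concurrent control against which to judge a background of low values.

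**Working it through.** **1. Baseline conditions in the SAP's threshold counts**

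- QTcF (2.7.4.1): the baseline must be missing or must not already meet the criterion.
- Liver tests (2.7.3): the text says openly that the baseline value is disregarded.
- Low cardiac function (2.7.4.1): the text says neither. Read literally, baseline is ignored.

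**2. Change-from-baseline summaries for the quantitative items in the endpoint bullet**

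- ECG intervals: specified (2.7.4.1).
- Vital signs: specified (2.7.4.2).
- Laboratory data: specified, with shift tables (2.7.3).
- Anthropometry: specified (2.7.4.3).
- Echocardiogram: not specified.

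SAP 2.1.2 nevertheless defines echocardiogram visit windows for both periods, and says such windows serve assessments summarized by visit. A count of children ever below a limit needs no windows. This points to an omission. SAP Section 1 says the SAP supersedes the protocol's statistical considerations and that substantial differences will be identified. Section 4 lists two changes, neither about echocardiography.

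**3. Baseline for the post-OAV101 output**

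SAP 2.1.1 fixes baseline for other assessments as the last value before the first Period 1 administration. A child randomized to sham whose LVEF first drops below 56% during the sham year, and stays there after OAV101, is counted as post-OAV101 low function. A new-onset rule using that same baseline would still call the child new. Separating the two needs the last echocardiogram before OAV101. For children first given sham this is normally Week 48: Table 8-1 schedules none at Week 52, and the SAP's Week 48 echocardiogram window runs to the day before the second administration.

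**4. Effect on the randomized table (illustration only)**

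The documents state no rate, power or test for this endpoint, so there is no plan figure to reproduce. Let *b* be the share below a limit at baseline, *r* the chance that such a child is low again after baseline, and *q* the new-onset rate among the rest. All three are assumed. Arm sizes of 75 and 50 are from SAP Section 3.

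Expected proportion counted = *b·r* + (1 − *b*)·*q*

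With *q* = 2% for sham and 10% for OAV101, the new-onset risk ratio is 0.10 / 0.02 = 5.0. Under the planned rule:

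| *b*, *r* | Sham | OAV101 | Risk ratio | Risk difference | Carried-in children (sham / OAV101) |
|---|---|---|---|---|---|
| 2%, 0.5 | 0.010 + 0.98 × 0.02 = 0.0296 | 0.010 + 0.98 × 0.10 = 0.108 | 3.65 | 7.8 points | 0.5 / 0.75 |
| 5%, 1 | 0.050 + 0.95 × 0.02 = 0.069 | 0.050 + 0.95 × 0.10 = 0.145 | 2.10 | 7.6 points | 2.5 / 3.75 |
| 10%, 1 | 0.100 + 0.90 × 0.02 = 0.118 | 0.100 + 0.90 × 0.10 = 0.190 | 1.61 | 7.2 points | 5.0 / 7.5 |

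Carried-in children are *n·b·r*. If *q* is equal in both arms the ratio is 1.0 for every *b* and *r*. The rule therefore pulls a true ratio towards 1 and creates no expected difference between arms.

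**5. How many counted children might have started low**

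A simulation assumed normally distributed LVEF with mean 62–66%, between-child SD 3–4, within-child SD 3 and six post-dose echocardiograms (Weeks 1, 4, 8, 12, 24 and 48), with no drug effect. It put 0.9–11.5% of children below 56% at baseline. Of the children ever below 56% afterwards, about 9–31% had been below it at baseline. The LVEF distribution is assumed, LVFS is left out, and the investigator exclusions are not modelled.

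**The case against.** **The endpoint is a status count by design.** A reader might infer that the rule contradicts an endpoint defined as change from baseline. It does not. Table 2-1 gives low cardiac function its own bullet, and protocol and SAP define it identically. The change-from-baseline bullet is a separate endpoint. This objection stands, and is why the defined count should stay.

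**The count does not create cardiac events.** A reader might also infer that children low at entry are reported as cardiac adverse events. SAP 2.7.1.1 identifies adverse events of special interest through a separate case retrieval strategy, which this count does not feed. A child low at entry but normal at every later echocardiogram is not counted at all. This stands too.

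**Absolute thresholds are ordinary in safety tables.** The liver counts disregard baseline, and the blood pressure flags set no baseline condition. This is fair, but liver and vital-sign data also get change-from-baseline summaries, so a reader can see where participants started.

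**The by-visit summary is already implied.** Protocol 12.5.2 promises it, and the SAP has windows for it. That is a reasonable reading of intent. Against it, the SAP says it supersedes the protocol's statistics, and its echocardiogram text specifies only the two counts. Adding the table carries out that intent.

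**A new-onset rule has limits.** Under the simulation's assumptions, 69–91% of counted children had a baseline at or above 56%, so most threshold crossings from measurement variation would remain. Used as a replacement, it would also drop a child who fell from 54% to 35%. Both points stand. The new-onset line should therefore be supplementary and accompanied by change data.

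**Conclusion.** The point holds as a reporting gap that should be closed. Two facts rest on the text alone: the count has no baseline condition, and SAP 2.7.4.1 specifies no output for the listed endpoint of change from baseline in echocardiogram, with no entry in Section 4. Together they leave pre-existing and new low function indistinguishable in the specified echocardiogram outputs. The consequence is greatest in the post-OAV101 output.

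It would be too strong to say that the randomized comparison is biased towards or against OAV101. Randomization gives both arms the same expected background, and the effect is dilution towards no difference. The risk ratios of 3.65 to 1.61 in place of 5.0 are illustrations on assumed rates. The true size is unknown, because the documents give no LVEF or LVFS distribution and do not show whether any enrolled child was below a limit at entry. No stated figure in the plan changes, and nothing here calls for altering the thrombus count.

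**What to change.** In SAP 2.7.4.1:

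1. Keep the protocol-defined low cardiac function count unchanged.
2. Add a supplementary new-onset count, limited to children whose baseline LVEF and LVFS were not below the limits or were missing, in line with the QTcF rule.
3. Add observed values and change from baseline in LVEF and LVFS by visit and arm, and a shift table of baseline against worst post-baseline category. The numeric change table is needed as well because a child who starts low and worsens shows only as low-to-low in a shift table.
4. In the post-OAV101 output, use the last echocardiogram before OAV101 as baseline for items 2 and 3.

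The cost is SAP wording and a few extra descriptive tables. The echocardiograms are already collected and centrally reviewed, so trial conduct does not change. Because the defined count is untouched, the additions create no departure from the protocol endpoint.
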